#### Notes:

- A participant with a positive IGRA [QFT-G] test result upon retest (after an initial indeterminate result) regardless if in endemic or non-endemic region should be referred to a TB-specialist for assessment to rule out active TB as described in protocol and initiation of appropriate latent TB treatment (with the assessment and treatment comprehensively documented in source) before any further IMP administration.
15. Any negative PCR or antigen test result (central or local labs as appropriate) at screening in addition to no known or suspected COVID-19 exposure within 2 weeks prior to screening based on the COVID-19 questionnaire.

- If there is a known or suspected exposure, a participant must be negative upon re-test result (central lab or local lab) obtained after 2 weeks and must remain asymptomatic for inclusion in the study.

Note: Following study specific rescreening procedures, participants positive at screening may be re-screened after 6 weeks of mild/asymptomatic infections or at the discretion of Investigator, provided there has been no development of severe COVID-19 disease or sequelae. Participants may also be re-screened a second time following rescreening procedures, if the primary reason for screen failure was due to positive COVID-19 test.

16. Willing to forego other forms of experimental treatment during the study.

#### **Weight**

17. Body weight  $\geq 40$  kg.

#### **Sex**

18. Contraceptive use by men or women should be consistent with local regulations regarding the methods of contraception for those participating in clinical studies.

##### **(a) Male participants:**

- All fertile males who are sexually active must use condom from Day 1 until at least 16 weeks after receipt of the final dose of IMP. It is strongly recommended that the female partner of a male participant also use an effective method of contraception from Table 2 (other than a barrier method) throughout this period.
- Men are considered fertile after puberty unless they have previously had bilateral orchidectomy or undergone vasectomy, which should be documented in the participant's medical records. Male participants must not donate sperm during the course of the study and for 16 weeks after the last dose of the investigational medicinal product.

##### **(b) Female participants:**

##### **Women of child-bearing potential (WOCBP)**

- Negative serum  $\beta$ -human chorionic gonadotropin ( $\beta$ -hCG) test at screening (females of childbearing potential only).
- Women of child-bearing potential must have a negative urine pregnancy test at randomisation (Day 1), prior to administration of investigational medicinal product.
- Females of childbearing potential must use 1 highly effective method of contraception, plus a male condom, from Screening until 16 weeks after the final dose of IMP, unless the participant is surgically sterile (e.g., bilateral oophorectomy or complete hysterectomy), has a sterile/non-fertile male partner, is at least 12 months postmenopausal, or practices sustained abstinence consistent with the participant's customary lifestyle. Highly effective methods of birth control include those listed in Table 2.

### **Women of non-childbearing potential**

- Women of non-childbearing potential must be postmenopausal or have been surgically sterilized (i.e., bilateral oophorectomy, or complete hysterectomy), which should be documented in the participant's medical records.
  - A post-menopausal state may be inferred for women not taking hormone replacement therapy (HRT) by a history of  $\geq 12$  months amenorrhoea and follicle stimulating hormone (FSH) levels in a sample collected during screenings in the laboratory's normal range for post-menopausal women.
    - A post-menopausal state may be inferred for women who are taking HRT and  $> 40$  years of age if:
      - Menopause was documented in medical records before initiation of HRT
- OR
- At least 2 FSH levels are within postmenopausal range while on the HRT

The table below lists highly effective methods of contraception. Female participants of childbearing potential must use one of the following non-hormonal or hormonal methods **along with a male condom**. Highly effective methods (those that can achieve a failure rate of less than 1% per year when used consistently and correctly) include:

**Table 2                      Highly effective methods of birth control**

Non-hormonal	
 
• Vasectomised partner (confirmed absence of sperm in semen)
 
• Bilateral tubal occlusion (caveat: failure rate <math>> 1\%</math>)
 
• Intrauterine device (copper)
 
• True sexual abstinence in line with the preferred and usual lifestyle choice of the participant
 

Hormonal	
 
• Intrauterine hormone-releasing systems (IUS)
 
• Combined (estrogen and progestogen containing) hormonal contraception associated with inhibition of ovulation – oral, intravaginal, or transdermal
 
• Progestogen-only hormonal contraception associated with inhibition of ovulation- oral (Cerazette only), injectable, or implantable
 

- Ineffective methods that should **not** be used are as follows:
  - Periodic abstinence (calendar, sympto-thermal, post-ovulation methods)
  - Coitus interruptus (withdrawal method)
  - Spermicides
  - Lactational amenorrhea
  - Non-copper containing intrauterine devices (or others not listed in the acceptable methods of contraception)
  - Some low dose or triphasic COCs (combined oral contraceptives)

- Progesterone only oral contraceptives (except Cerazette)
- Sponge, diaphragm, male or female condoms without secondary methods

### 3.2 Exclusion criteria

Participants should not enter the study if any of the following exclusion criteria are fulfilled.

#### Medical Conditions

1. History of, or current diagnosis of, a clinically significant non-SLE related vasculitis syndrome (see [Appendix J](#)). Vasculitis due to SLE is allowed in the study.
2. History or evidence of suicidal ideation (severity of 4 [active: method and intent, but no plan] or 5 [active: method, intent, and plan]) within the past 6 months; or any suicidal behavior within the past 12 months or recurrent suicidal behaviour in the lifetime of the participant based on an assessment with the C-SSRS ([Appendix Q](#)) at screening or at baseline.
3. Active severe or unstable neuropsychiatric SLE including, but not limited to aseptic meningitis; cerebral vasculitis; myelopathy; demyelination syndromes (ascending, transverse, acute inflammatory demyelinating polyradiculopathy); acute confusional state; impaired level of consciousness; psychosis; acute stroke or stroke syndrome; cranial neuropathy; status epilepticus; cerebellar ataxia; and mononeuritis multiplex:
  - (a) Where, in the opinion of the Principal Investigator (PI), delegated Sub-Investigator (SI) or Sponsor, protocol specified standard therapy is insufficient and utilization of a more aggressive therapeutic approach, such as adding IV cyclophosphamide and/or high dose IV pulse corticosteroid therapy or other treatments not permitted in the protocol, is indicated.
4. Active severe SLE-driven renal disease where, in the opinion of the PI or delegated SI or Sponsor, protocol specified standard therapy is insufficient and utilization of a more aggressive therapeutic approach, such as adding IV cyclophosphamide and/or high dose IV pulse corticosteroid therapy or other treatments not permitted in the protocol, is indicated.
5. Diagnosis (within 1 year of signing the ICF) of mixed connective tissue disease or any history of overlap syndromes of SLE and systemic sclerosis (SSc), as noted in (a) or (b) below:
  - (a) An overlap syndrome of SLE with myositis or rheumatoid arthritis at Screening is permitted provided the participant also meets the criteria for the classification as SLE; or
  - (b) A history of mixed connective tissue disease, which over time has developed into a diagnosis of SLE, is permitted provided diagnosis of SLE has been present for at least 1 year.

6. History of, or current diagnosis of, catastrophic anti-phospholipid syndrome (APS) within 1 year prior to signing the ICF. Participants with other degrees of APS adequately controlled by anticoagulants or aspirin for at least 12 weeks can be recruited to the study.
7. History of, or current, inflammatory joint or skin disease other than SLE that, in the opinion of Investigator, could interfere with the inflammatory arthritis or skin assessments and confound the disease activity assessments.
8. History of any non-SLE disease that has required treatment with oral or parenteral corticosteroids for more than a total of 2 weeks within the last 24 weeks prior to signing the ICF.

**Exclusion criteria related to infection and malignancy risk factors**

9. History of recurrent infection requiring hospitalization and IV antibiotics (e.g., 3 or more of the same type of infection over the previous 52 weeks).
10. Known history of a primary immunodeficiency, splenectomy, or any underlying condition that predisposes the participant to infection, or a positive result for human immunodeficiency virus (HIV) infection confirmed by central laboratory at Screening.
  - (a) An HIV test must be performed during screening, and the result should be available prior to randomisation. The participant is ineligible to participate in the study when positive for HIV antibody or infection (i.e., positive nucleic acid test) performed by the central laboratory. Participants refusing HIV testing during the screening period will not be eligible for study participation.
11. At Screening, confirmed positive test for hepatitis B serology, as confirmed by central laboratory, for:
  - (a) Hepatitis B surface antigen (HBsAg);Or
  - (b) Hepatitis B core antibody (HBcAb) and hepatitis B virus (HBV) DNA detected above the lower limit of quantitation (LLOQ) by reflex testing by the central laboratory at screening.

Note: Participants who are HBcAb positive at screening will be tested every 3 months for HBV DNA. To remain eligible for the study, the participant's HBV DNA levels must remain below the LLOQ as per the central laboratory.
12. Active hepatitis C infection (defined as positive hepatitis C virus [HCV] antibody and detectable HCV RNA as confirmed by central laboratory).
13. Any severe case, as defined by study guidelines, of herpes zoster infection at any time prior to Week 0 (Day 1), including, but not limited to, non-cutaneous herpes (ever), herpes encephalitis (ever), recurrent herpes zoster (defined as 2 episodes within 2 years) or ophthalmic herpes involving the retina (ever).

Any herpes zoster infection that has not completely resolved within 12 weeks prior to signing the ICF.

14. Any clinical cytomegalovirus (CMV) or Epstein-Barr virus infection that has not completely resolved within 12 weeks prior to signing the ICF.
15. Opportunistic infection (see section 6.3.2) requiring hospitalization or IV antimicrobial treatment within 3 years of randomisation.
16. Any history of severe COVID-19 infection (e.g., prolonged hospitalization [hospitalization for observational purposes is not exclusionary]) or any prior COVID-19 infection with documented long COVID and/or clinically significant unresolved sequelae.
17. Any mild/asymptomatic COVID-19 infection (lab confirmed or suspected based on clinical symptoms) within the last 6 weeks prior to first dosing.
18. Any of the following:
  - (a) Clinically significant chronic infection (i.e., osteomyelitis, bronchiectasis, etc) within 8 weeks prior to signing the ICF (chronic nail infections are allowed).
  - (b) Any infection requiring hospitalization or treatment with IV anti-infectives not completed at least 4 weeks prior to signing the ICF.
19. Any infection requiring oral anti-infectives (including antivirals) within 2 weeks prior to Day 1.
20. History of cancer, apart from:
  - (a) Squamous or basal cell carcinoma of the skin treated with documented success of curative therapy  $\geq 3$  months prior to Week 0 (Day 1)
  - (b) Cervical cancer in situ treated with apparent success with curative therapy  $\geq 1$  year prior to Week 0 (Day 1).
21. Females with abnormal cervical cancer screening results as specified in Appendix H:
  - (a) All females who have been or are sexually active with an intact cervix must have documentation of a normal cervical cancer screening (Pap smear or HPV tests as per local guidelines) result within 2 years prior to randomisation. Any abnormal cervical cancer screening result documented within 2 years prior to randomisation must be repeated to confirm participant eligibility.
  - (b) Females aged  $< 25$  years, who have never been sexually active or have well-documented HPV vaccination records may not require a cervical cancer screening test.

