#### **5.2.2.3 Cervical Cancer Screening Test (Pap Smear/HPV Test)**

Most cases of cervical cancer appear to be related to infection with papilloma virus. Because of the potential for viral reactivation due to blockade of the interferon pathway, we are

assessing cervical dysplasia in this study, although to date there has been no signal in the anifrolumab studies.

A Cervical Cancer Screening Test (Pap smear/HPV test which is in align with local practice) is required at screening in women who have not had their cervix surgically removed. If a Cervical Cancer Screening Test was performed within 2 years prior to screening with no documented malignancy (e.g., cervical intraepithelial neoplasia grade III [CIN III], carcinoma in situ [CIS], or adenocarcinoma in situ [AIS]) or no High-risk HPV was found, it does not need to be repeated. Abnormal Cervical Cancer Screening Test results received anytime within the 2 years prior to randomisations must be repeated to ensure eligibility. Please refer to [Appendix H](#) for guidance.

Participants should have a Pap Smear or HPV Test at the end of treatment per local standard of care, if possible, between Week 48 and Week 52, to ensure that there is no evidence of new cervical dysplasia. Since access to a Pap Smear or HPV Test may vary by county, the Sponsor recommends that local guidelines for obtaining Pap Smear or HPV Test in participants who have received immunomodulators or immunosuppressive treatment be followed. If a Pap Smear was performed at the EOT was not normal but showed no evidence of malignancy (e.g., CIN III, CIS or AIS), it should be repeated as per the participant's gynaecologists recommendation. If the participant's gynaecologist has recommended a repeat Pap Smear be performed at a specified interval, the Pap Smear should be obtained as recommended and the report provided in source document.

Females aged < 25 years, who have never been sexually active or have well documented HPV vaccination records may not require a cervical cancer screening test.

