## Appendix H Guidance for Cervical Cancer Testing Results

### Guidance for Abnormal Pap Smear Results

Pap Smear Result	Abbreviation	Also Known As	Suggested Action
Atypical squamous cells–undetermined significance	ASC–US	—	Permitted to enter study
Atypical squamous cells–cannot exclude HSIL	ASC–H	—	Permitted to enter study
Atypical glandular cells	AGC	—	Permitted to enter study
Low-grade squamous intraepithelial lesion	LSIL	Mild dysplasia Cervical intraepithelial neoplasia–1 (CIN–1)	Permitted to enter study
High-grade squamous intraepithelial lesion	HSIL	Moderate dysplasia CIN–2 / CIN II	Permitted to enter study
High-grade squamous intraepithelial lesion	HSIL	CIN–3 / CIN III Carcinoma in situ (CIS)	Exclude/discontinue participant
Endocervical adenocarcinoma in situ	AIS	—	Exclude/discontinue participant

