### Guidance for HPV Test Results

Test Result	Interpretation	Suggested Action
Negative HPV test result	High-risk HPV was not found	Permitted to Enter Study
Positive HPV test result	High-risk HPV was found	Exclude/discontinue participant

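### The cervical screening rules in exclusion 21(a), Section 5.2.2.3 and Appendix H do not agree for most abnormal Pap results, and HSIL without a CIN grade has no single action

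*Protocol*

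**What the plan says.** Three places in the protocol govern one screening test.

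- **Section 3.2, exclusion 21.** The lead-in excludes "Females with abnormal cervical cancer screening results as specified in Appendix H". Item (a) then says that women with an intact cervix who are or have been sexually active "must have documentation of a normal cervical cancer screening (Pap smear or HPV tests as per local guidelines) result within 2 years prior to randomisation". It adds: "Any abnormal cervical cancer screening result documented within 2 years prior to randomisation must be repeated to confirm participant eligibility". Item (b) exempts some women under 25.
- **Section 5.2.2.3.** One sentence sets an exemption. It begins "If a Cervical Cancer Screening Test was performed within 2 years prior to screening with no documented malignancy", gives CIN III, CIS and AIS as examples, and ends "or no High-risk HPV was found, it does not need to be repeated". The next sentence reads: "Abnormal Cervical Cancer Screening Test results received anytime within the 2 years prior to randomisations must be repeated to ensure eligibility". The paragraph then points to Appendix H for guidance.
- **Appendix H.** The Pap table is titled as guidance on abnormal results, and its action column is labelled as a suggestion. ASC-US, ASC-H, AGC, LSIL and HSIL/CIN-2 are permitted to enter. HSIL/CIN-3/CIS and AIS lead to exclusion or discontinuation. The result name "High-grade squamous intraepithelial lesion" heads two rows, told apart only by the CIN grade in the synonym column. In the separate HPV table, a positive test ("High-risk HPV was found") leads to exclusion or discontinuation.

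No passage says which of the three prevails.

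**The concern.** An eligibility rule has to give one answer for each result a laboratory can report. Here the mandatory criterion asks for a normal result, while the appendix it cites admits five kinds of abnormal result. The repeat instruction does not settle the matter, because the protocol does not say what the repeat must show.

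Section 5.2.2.3 gives a safety reason for the test: blocking the interferon pathway might allow viral reactivation, although it notes that no signal has been seen so far. As written, whether a woman with a given abnormal smear is exposed to study drug can depend on which sentence the site applies.

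There is also a consequence for reporting. Section 3 of the protocol forbids eligibility waivers, and Section 3.4 allows no exceptions. SAP Section 3.3.5 makes exclusion-criteria deviations a category of important protocol deviation. An investigator who admits a woman because Appendix H permits her result can therefore be recorded as having broken exclusion 21(a).

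**Working it through.** There is no figure to reproduce. The check is to take each possible prior result through the three passages.

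| Prior result | Exclusion 21(a) | Appendix H | 5.2.2.3, exemption sentence | 5.2.2.3, next sentence | Do they agree? |
|---|---|---|---|---|---|
| Normal Pap, or negative HPV | Meets it | Negative HPV permitted; a normal Pap is not listed | No repeat | Not triggered | Yes, apart from the time window |
| ASC-US, ASC-H, AGC, LSIL | Not normal; repeat | Permitted | No repeat | Repeat | No |
| HSIL with CIN-2 | Not normal; repeat | Permitted | No repeat | Repeat | No |
| HSIL, no CIN grade | Not normal; repeat | Fits one permitting row and one excluding row | Unclear | Repeat | Undetermined |
| HSIL with CIN-3 or CIS; AIS | Not normal; repeat | Exclude | Not exempt | Repeat | Yes |
| Positive high-risk HPV | Not normal; repeat | Exclude | Not exempt | Repeat | Yes |

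**Count.** The Pap table has seven rows. Five of them (ASC-US, ASC-H, AGC, LSIL, HSIL/CIN-2) conflict with 21(a). The other two (HSIL/CIN-3/CIS and AIS) do not. Ungraded HSIL has no row of its own.

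**One case followed through.** Take a woman with LSIL one year before randomisation.

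1. Under 21(a) her result is not normal, so she must be re-tested.
2. Under the exemption sentence of Section 5.2.2.3 she need not be, because no malignancy is documented.
3. Under the next sentence of Section 5.2.2.3 she must be.
4. Suppose she is re-tested and LSIL is found again. Exclusion 21(a) still asks for a normal result, Appendix H still permits entry, and nothing says which decides.

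**Time window.** The exemption in Section 5.2.2.3 counts 2 years back from screening. Exclusion 21(a) counts 2 years back from randomisation, as does the Table 3 footnote on this test. Screening can last up to 35 days. A test done almost 2 years before screening can thus be up to about 35 days outside the 21(a) window on Day 1, yet be exempt from repeat under Section 5.2.2.3. This applies even to a normal result.

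**The case against.** The strongest defence is that Appendix H governs. The lead-in to exclusion 21 defines the excluded results by reference to it, and Section 5.2.2.3 refers to it too. If abnormal is read to mean only the results that Appendix H excludes, most of the text fits together: the exemption threshold in Section 5.2.2.3 matches the excluding rows, and the repeat sentences would apply only to those.

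That reading does not hold. The Pap table in Appendix H calls all its entries abnormal, including those it permits. Exclusion 21(a) uses the word normal with a mandatory verb, whereas Appendix H offers suggested actions. No order of precedence is given.

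Several stronger readings are tempting, and the documents do not support them:

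- *Appendix H contradicts itself on HSIL.* It separates its two HSIL rows by CIN grade. The gap exists only when no grade is reported.
- *A woman with LSIL fails 21(a) outright.* She is sent for a repeat first. What is open is the standard the repeat must meet.
- *Section 5.2.2.3 is a third eligibility threshold.* Its two sentences say when to repeat a test. They conflict with each other on that.
- *Different Pap and HPV tables are in themselves a contradiction.* The choice of test is expressly left to local guidelines. That is a design choice, and the rules agree for a positive HPV result. A count of HPV-positive women would therefore not measure this problem.
- *Sites already differ, or the treatment comparison is biased.* The documents report no such event. The safety analyses in SAP Section 4.6 include no cervical screening endpoint.

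**Conclusion.** The inconsistency is real and stands in current protocol text. It does not come from redaction or from the amendment history. It covers five abnormal Pap categories, HSIL without a CIN grade, and a mismatch of up to about 35 days between two time windows. Women with the same abnormal Pap result can be handled differently, and following one part of the protocol can be recorded as a deviation from another.

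The number of women affected cannot be estimated, because the documents give no frequency for any Pap result. Different handling between sites is an inference from the wording. The conclusion assumes that normal in 21(a) carries its ordinary meaning and that no unseen site instruction settles the order of precedence. Sample size, power and type I error are unaffected. This should be corrected, but it does not threaten the primary analysis.

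**What to change.** Reconcile exclusion 21(a), Section 5.2.2.3 and both tables of Appendix H:

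- Give each reportable result, including HSIL without a CIN grade, exactly one eligibility action and one repeat rule.
- State what a repeat result must show for the woman to be eligible.
- Remove the conflict between the two adjacent repeat sentences in Section 5.2.2.3.
- Use one reference date for the 2-year window throughout.
- Say which passage prevails if any overlap remains.

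Which clinical rule to adopt is for the sponsor's medical team.

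The cost is protocol wording in three places. Making the rules agree needs no new test or visit in itself. The documents do not give recruitment status. If recruitment has already closed, the decision is still needed: SAP Section 3.3.5 requires the list of important deviations to be final before database lock and unblinding, and these women cannot be classified consistently until it is settled which rule applied to them.
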